Number of Participants with Rationale:	N = 30 (10 participants per researcher). Both conditions will be measured for each participant. This sample population will provide an adequately powered study under the assumption that time variance of each condition is within approximately 5 minutes.		

SRF-371

Confidential and proprietary.

This document and its contents are confidential and proprietary to Sonova and shall not be reproduced or otherwise disclosed to anyone other than Sonova employees without written authorization from Sonova.

This printout is an uncontrolled copy. The original is stored in the Document Management System  
Template: TPL-368 [2]

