##### 6.1.2 Measures for minimizing bias

Conditions will be counterbalanced across participants. In addition, three research audiologists will be involved in data collection in order to better represent the skill level of an average provider.

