### 6.4 Procedures

#### 6.4.1 Investigation-related Procedure

Three researchers will be facilitating these appointments to limit variability of researcher skill across the two conditions. Researchers will familiarize themselves with the [REDACTED] equipment through independent practice prior to a training facilitated by [REDACTED] (occurring April 23rd) and the researchers will follow [REDACTED] training recommendations (perform scans on 20+ ears following in-person training) prior to data collection. Participants will be seen for one appointment. REUR/REUG, RECD, tympanometry, and reflex thresholds will be collected. The researcher will perform both traditional earmold impressions and 3D ear scans on both ears (conditions will be randomized and counterbalanced across participants). An additional researcher will use a stop watch to quantify the time (mm:ss) it takes for each condition, for both ears. After each procedure, participants and the clinician will also be asked to complete a questionnaire regarding each condition, focusing on their perception of comfort and level of involvement throughout the impression taking. In the event that a clinician feels as though a silicone impression needs to be remade, this will be recorded on the clinician questionnaire. Timing will be recorded for all attempts, but only the time recorded for the final impressions will be used in the data analysis. The resulting data will be compiled for all participants and analyzed using a T-test, to identify any significant differences in the time it takes to complete each method of earmold impressions, in addition to any differences in perceptual comfort.

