#### 7.3.1 Datasets to be analyzed, analysis population

Total procedure time will be recorded in seconds. Each procedure time will be recorded along with the audiologist, the anonymous participant ID, the procedure methodology (i.e., scanning or traditional silicone impressions), and the ordinal number of the procedure for the given methodology by the respective audiologist. Qualitative data will be collected as a question, response, methodology, and anonymous participant ID.

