## Clinical Investigation Plan (CIP)

each methodology will be tested for normality using a Shapiro-Wilk test. If the data are normally distributed, additional analysis will proceed immediately. If data are not normally distributed, transformation(s) may be performed on the data, as appropriate, to achieve an approximately normal distribution of the response data for further analysis.

Data (raw or transformed, per above) will then be subjected to analysis via linear mixed effects modeling. The model will be constructed to regress (raw or transformed) procedure time on a dummy variable of methodology (fixed effect), with a random effect of audiologist. This model will allow the investigators to evaluate the relative difference in procedure time between the methodologies, while removing and separately evaluating the variance contributed by the audiologist undertaking the procedure.

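### Three audiologists cannot give an interpretable audiologist variance, and the primary model does not assess whether the scan-minus-silicone difference varies between them

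*Combined protocol and SAP*

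**What the plan says.** Section 7.3.2 regresses procedure time, raw or transformed, "on a dummy variable of methodology (fixed effect), with a random effect of audiologist". It says the model gives the relative difference between methods while "removing and separately evaluating the variance contributed by the audiologist undertaking the procedure". No method-by-audiologist term, random slope or participant term is stated.

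The synopsis gives the layout: "N = 30 (10 participants per researcher). Both conditions will be measured for each participant". Method is crossed with audiologist, since section 6.4.1 says "The researcher will perform both traditional earmold impressions and 3D ear scans on both ears". Section 6.1.2 explains the number of audiologists: "three research audiologists will be involved in data collection in order to better represent the skill level of an average provider".

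Section 7.3.1 records the audiologist, participant ID and method with each time, and also "the ordinal number of the procedure for the given methodology by the respective audiologist". The only other look at audiologists is in section 7.3.3, an optional visual check of learning curves that is not a statistical analysis. Sections 5.3, 5.5 and 7.1 call the study exploratory. Sections 5.1 and 5.2 nevertheless set out to identify significant differences in time.

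**The concern.** There are two linked problems.

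1. **The promised variance.** Three levels carry very little information about a variance. A reported value, and a value of zero in particular, could be read as showing that audiologists did or did not differ when the data cannot say.

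2. **The missing term.** A random intercept describes whether an audiologist is faster or slower overall. It does not describe whether the gain or loss from scanning differs between audiologists, which is what bears on other providers. The plan makes such variation plausible: silicone impressions are within the audiologists' existing scope of practice (section 4.5), while the scanner calls for training and practice scans (sections 2.8 and 6.4.1).

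The result is meant to inform adoption in Audiological Care clinics (sections 4.1 and 5.1). One quick or slow adopter among three people could shift the overall difference considerably, and no planned statistical analysis would show it.

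**Working it through.** **Inputs from the documents.** 3 audiologists × 10 participants = 30 participants, which matches the stated N. Two methods each give 60 times, 20 per audiologist. Section 7.1 says no sample size calculation was done, so there is no power figure to reproduce.

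**Assumptions, because the documents give no values.** Two-sided 5% test; untransformed times; complete data; SD of the paired difference 5 min, hence residual SD σ = 5/√2 = 3.5 min. The synopsis mentions about 5 minutes for each condition, but that is not an SD of the paired difference. The intraclass correlation (ICC), the between-audiologist SD of the method difference (τ) and the participant SD (σp) are shown as ranges.

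**Step 1: precision of the audiologist variance.** Suppose each audiologist's true mean were known exactly. The 95% interval for the variance is then the estimate times 2/χ²(0.975; 2) to 2/χ²(0.025; 2), that is 2/7.378 = 0.27 to 2/0.0506 = 39.5. For the SD the multipliers are 0.52 to 6.3. Ten audiologists would give 0.47 to 3.3 for the variance.

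**Step 2: chance of a zero estimate.** In the balanced layout the REML estimate is zero when the audiologist mean square does not exceed the residual mean square. With r = ICC/(1 − ICC), the probability is P(F(2, 56) < 1/(1 + 20r)).

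| ICC | 1/(1 + 20r) | P(estimate = 0) |
|---|---|---|
| 0.05 | 0.487 | 38% |
| 0.10 | 0.310 | 27% |
| 0.20 | 0.167 | 15% |

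With no audiologist variance at all it is 63%, so a zero estimate says little.

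**Step 3: is it estimable?** Yes. With a true variance of 0.25 and residual variance 1 (ICC 0.20), 200 of 200 simulated REML fits returned a value. The median was 0.17, the 95% range 0.00 to 1.14, and 13% were near zero.

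**Step 4: type I error if the result is read for an average provider.** The true variance of the mean difference is τ²/3 + 2σ²/30 = τ²/3 + 0.833. The planned model has no participant term, so its squared standard error averages about 2(σ² + σp²)/30. That is 0.833 if σp = 0 and 1.667 if σp = σ. Approximately, type I error = 2[1 − Φ(1.96 √(model variance / true variance))].

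- τ = 1, σp = 0: √(0.833/1.167) = 0.845, giving 9.8%.
- τ = 2, σp = 0: √(0.833/2.167) = 0.620, giving 22.4%.
- τ = 1, σp = σ: √(1.667/1.167) = 1.195, giving 1.9%.
- τ = 2, σp = σ: √(1.667/2.167) = 0.877, giving 8.6%.

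Simulating the planned model itself, with its t reference distribution and variance truncated at zero, gives:

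| τ (min) | σp = 0 | σp = σ/2 | σp = σ |
|---|---|---|---|
| 0 | 5% | 3% | 1% |
| 1 | 9% | 6% | 2% |
| 2 | 20 to 21% | 16% | 8 to 9% |

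**Step 5: what an average-provider test would cost.** Testing the three audiologist mean differences against their own spread holds the type I error at 5%, but on 2 df. The critical value rises from 2.00 (56 df) to 4.30. With no interaction and no participant effect, power for a difference of one residual SD falls from 0.97 to 0.54.

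**Step 6: precision per audiologist.** From ten pairs and an SD of 5 min, the half-width is 2.262 × 5/√10 = 3.6 min. Pooling the SD over audiologists (27 df) gives 2.052 × 5/√10 = 3.2 min.

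**The case against.** The strongest reply is that the study is exploratory, sets no precision target for the audiologist variance, and already has its primary quantity in the model. Much of this stands, and it rules out four stronger readings.

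- **A reader might infer that the variance cannot be estimated.** It can (step 3). The defect is imprecision.
- **A reader might infer that the model omits the primary quantity.** It does not. The mean difference between methods is the fixed effect and answers the primary objective in section 5.2. What is missing is how that difference varies between audiologists.
- **A reader might infer that the audiologist intercept does nothing.** It cancels from the estimated method difference in the balanced layout. But it does take overall audiologist differences out of the residual, so the removing half of the promise is met.
- **A reader might infer that the confidence interval is simply too narrow.** That follows only for an average-provider reading, and only for some values of τ and σp. With substantial participant variance the unpaired standard error makes the test conservative. The two omissions can offset each other, but nothing in the plan ensures that they do.

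The average-provider wording appears under bias control in section 6.1.2, and section 7 makes no formal inference to a population of providers. Sections 6.4.1 and 6.4.3 give other reasons for using three researchers. The optional learning-curve plot might also reveal an outlying audiologist. These points lower the weight of the concern. They do not remove it, because the plan still seeks significant differences to inform use in clinics, and the plot is neither required nor a comparison of methods.

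**Conclusion.** The concern holds in a limited form and is worth acting on. The separate evaluation of audiologist variance promised in section 7.3.2 will not be informative: on 2 df the interval spans 0.27 to 39.5 times the estimate, and zero estimates are common at modest ICCs. This depends only on the number of audiologists and, for the zero estimates, on the assumed ICC.

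The plan also has no statistical assessment of whether the method difference varies between audiologists, although the crossed design and the recorded data allow one. The effect on the type I error is conditional. It is roughly 1% to 21% across τ of 0 to 2 min and participant SD from zero to the residual SD, given an assumed paired-difference SD of 5 min. It concerns only conclusions about providers beyond these three. As the study is exploratory, this is an improvement to the analysis and its wording, and it does not invalidate the primary comparison.

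**What to change.** In section 7.3.2:

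- Fit method, audiologist and method-by-audiologist as fixed effects, with a participant random effect for the paired times.
- Define the overall method difference as the equally weighted mean of the three audiologist-specific differences, so that it does not depend on the coding of the interaction.
- Report the difference with a 95% CI for each audiologist beside the overall one, as descriptive results. At about ±3.6 min each under the assumed SD, they will not resolve differences between audiologists of 1 or 2 min, and the report should say so.
- Delete the promise to evaluate audiologist variance separately.
- State there and in section 6.1.2 that the overall inference applies to these three research audiologists.

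**Cost.** No new data are needed, since section 7.3.1 already records audiologist, participant and method. For the paired comparison, the interaction takes 2 df (30 − 3 = 27 instead of 29). The main cost is a narrower stated generalisation. Keeping the average-provider claim would instead require the 2-df test in step 5, with its loss of power, or more audiologists.

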### 7.3.3 Secondary Analysis

Qualitative data acquired via questionnaires will not be statically analyzed. A cursory (i.e., visual) analysis of the “learning curve” for each audiologist may also be performed, but will not be included as a statistical analysis.

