## Clinical Investigation Plan (CIP)

### 1.3 Overall synopsis of the clinical investigation

Background and Rationale	
████████ claims the █████ 3D ear scanning solution to streamline clinical processes. According to █████, with the █████, you can:
 
 
• save time and money on handling earmolds and hearing aids
 
• secure digital patient records for easy storage, retrieval and use
 
• ensure a better fit and reduce remakes and returns,
 
• enjoy a cleaner procedure
 
 
████████ ████████ ████████
																	
	
Previous research has been done at Sonova HQ to analyze the quality of █████ ear scans compared to traditional earmold impressions. However, to fully understand the value drivers, further data is needed exploring efficiency and preferences in comparison to traditional EMI methods. In addition, the department of Audiological Care is interested in finding out if this is a viable piece of equipment for their clinics. The results of previous research regarding quality of the █████ has warranted a further look into efficiency and subjective preference.
																	
Investigation Objectives	
The primary objective of this study is to identify any significant differences in the time required for a clinician to complete the workflow of an █████ impression compared to traditional earmold impressions.
 
The secondary objective of this study is to identify any significant preference for both the HCPs and patients when comparing the █████ to traditional EMI procedures.
																	
Outcome(s) / Endpoints:	
Time (mm:ss) will be recorded to quantify the duration of each impression procedure.
 
Questionnaires will be administered to assess overall preferences of both the researchers and subjects.
																	

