## Clinical Investigation Plan (CIP)

	Number of Arms: [2]		
	 Observational Study		
	Investigation Model		Time Perspective
	 Cohort	 Ecologic	 Retrospective
	 Case-Control	 Family-based	 Prospective
	 Case-only	 other:	 Cross-sectional
	 Case-crossover		 other:
	Number of Groups/ Cohorts: [1]		
Type of design	 Exploratory	 Confirmatory	 Observational
Inclusion / Exclusion criteria:	External auditory canal must be present and medically unremarkable to facilitate impressions. Participants with surgical ears or without external auditory canals must be excluded.		
Measurements and procedures:	Three researchers will be facilitating these appointments to limit variability of researcher skill across the two conditions. Researchers will familiarize themselves with the [REDACTED] equipment through independent practice prior to a training facilitated by [REDACTED] (occurring April 22nd) and will follow [REDACTED] training recommendations (perform scans on 10+ ears following in-person training) prior to data collection. Participants will be seen for one appointment. The researcher will perform both traditional earmold impressions and 3D ear scans on both ears (conditions will be randomized and counterbalanced across participants). An additional researcher will use a stop watch to quantify the time (mm:ss) it takes for each condition, for both ears. At the end of the appointment, participants will also be asked to complete a subjective questionnaire regarding each condition, focusing on their perception of comfort and level of involvement throughout the impression taking. The resulting data will be compiled for all participants and analyzed using a T-test, to identify any significant differences in the time it takes to complete each method of earmold impressions, in addition to any differences in subjective domains.		
Intervention:	[REDACTED] 3D Ear Scanning Solution		
Control Intervention (if applicable):	Traditional silicone earmold impression material, administered by a cartridge impression gun.		

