#### 5.2 Primary and Secondary Objectives

The Primary objective is to identify any significant differences in the time required for a provider to complete the workflow of an [REDACTED] 3D ear scanner, compared to traditional silicone earmold impression procedures. The secondary objective is to identify any significant preferences for both providers and patients.

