## 7.4 Handling of missing data and drop-outs

Participants with missing procedure time data for either or both methodologies will be excluded from statistical analysis entirely. Missing qualitative data will not impact statistical analysis (as no statistical analysis is planned for qualitative data). Drop-outs will not be replaced during this study. Achieved statistical power will be calculated and documented if the planned sample size is not achieved.

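### The secondary objective (patient and provider preference) has no consistent analysis: some sections seek significance and extend a T-test to subjective data, while 7.3.3, 7.4 and 8.1.1 rule out any statistical analysis of the questionnaires

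*Combined protocol and SAP*

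**What the plan says.** All references are to the combined protocol and SAP.

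- **Objective.** Section 1.3 (Investigation Objectives): "The secondary objective of this study is to identify any significant preference for both the HCPs and patients". Section 5.2: "The secondary objective is to identify any significant preferences for both providers and patients". The matching endpoint line in 1.3 reads "Questionnaires will be administered to assess overall preferences of both the researchers and subjects".
- **Procedures.** Section 6.4.1 says the compiled data will be "analyzed using a T-test, to identify any significant differences" in procedure time, "in addition to any differences in perceptual comfort". The parallel sentence in 1.3 (Measurements and procedures) also names a T-test for time and ends "in addition to any differences in subjective domains". The two sentences differ in how much subjective data they cover.
- **Statistics and data handling.** Section 7.3.3: "Qualitative data acquired via questionnaires will not be statically analyzed". Section 7.4 confirms that "no statistical analysis is planned for qualitative data". Section 8.1.1 says questionnaire data will be compiled without statistical analysis.
- **Administration time.** Section 1.3 has participants complete the questionnaire when the appointment ends. Section 6.4.1 has participants and the clinician complete one after each procedure, and the step list for each method ends with the questionnaires.

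**The concern.** Section 3.2 names comfort and overall preference, for patients and providers, among the value drivers behind the clinics' decision on the scanner. The plan gives no single account of how those data will be turned into a finding. Under 7.3.3 they would be reported without any statement of uncertainty, and that section specifies no scoring or summary in place of a test. Under 1.3 and 6.4.1 they would be tested. No clause says which section prevails, and the opening of chapter 7 describes the statistical design as in line with chapters 5 and 6. The team could therefore test or not test after seeing the responses and cite the plan either way.

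**Working it through.** The check is textual: does any reading of the key words bring the sections into agreement?

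**1. *Significant* read statistically.** The T-test sentences use the word this way for time. On this reading 1.3 and 5.2 require an inferential result on preference. Sections 7.3.3, 7.4 and 8.1.1 exclude one, so the objective cannot be met.

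**2. *Significant* read loosely, as noteworthy.** This suits 5.1 and 5.5, which speak only of identifying preferences, and 7.1, which disclaims any aim of confirming effects. The objective can then stand beside 7.3.3. The T-test sentences in 1.3 and 6.4.1 still reach subjective data, so a conflict remains.

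**3. *Qualitative* read as free text only.** This would leave scaled items open to a test. But 7.3.1 records qualitative data as question, response, methodology and participant ID, and 8.1.1 refers to questionnaire data without exception. The reading fails.

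**4. Administration time.** One questionnaire at the end of the visit allows direct comparison and relies on recall. A questionnaire after each procedure gives a response close to each method, and the first is given before the second method has been experienced. The two schedules may not give the same responses. A direct question on overall preference can be answered only after both procedures.

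**5. Precision, for illustration.** The plan has no figure to reproduce here: it gives no alpha, power or sample size for the questionnaires, and the power remark in 1.3 concerns time. The response scales and the number of items are not given either. The input from the plan is 30 participants, 10 per researcher, each measured under both methods (1.3).

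- *Scaled item.* Assume a numeric rating and independent pairs. The 95% half-width, in SD of the within-participant differences, is t(0.975, n−1)/√n. For n = 30: 2.045/5.477 = 0.37. With 3 or 6 incomplete pairs (assumed), n = 27 gives 2.056/5.196 = 0.40 and n = 24 gives 2.069/4.899 = 0.42.
- *Direct choice.* Assume every participant chooses one method and that choices are independent. The approximate half-width at an even split is 1.96 × √(0.25/30) = 0.18, or 18 percentage points.
- *Providers.* If each of the three researchers gave one overall choice (assumed), the smallest possible two-sided exact p-value would be 2 × 0.5³ = 0.25.

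The patient figures ignore the nesting of 10 participants within each clinician. Section 7.3.2 models audiologist variance for time, so the same clustering could affect the responses.

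**The case against.** The strongest defence is that this is an exploratory study whose designers chose not to test the questionnaires and said so in three places, including both chapter 7 sections that deal with them. The T-test sentence looks like leftover wording: it also differs from the mixed model that 7.3.2 specifies for time, and in it *significant* attaches to time while the subjective clause mentions only differences. Leaving questionnaires untested is a legitimate choice, and wording changes alone would remove the contradiction.

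Much of this stands. It limits the weight of the point and makes a wording-only repair acceptable. It does not remove the point, because no precedence clause exists and the plain reading of 1.3 and 6.4.1 still applies a test that 7.3.3 excludes.

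A reader might infer more than the documents support:

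- *That objective, procedures and statistics are wholly incompatible.* The clash between the objective and 7.3.3 depends on reading *significant* statistically. Only the clash between the T-test sentences and 7.3.3 survives both readings.
- *That the plan carries a known false-positive rate.* One 5% test on each of the three patient domains named in 6.1.3 (comfort, involvement, confidence) would give 1 − 0.95³ = 14.3% if independent. That list is expressly open, however, and 6.4.1 extends the test only to comfort, perhaps a single test at 5%.
- *That an interval for providers would be too wide to use.* The spread between clinicians is unknown, so this cannot be shown. Having only three clinicians is reason enough to describe their responses.
- *That the two questionnaire schedules certainly yield different ratings.* The documents support only that they may.

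**Conclusion.** The point holds as a reconciliation of wording with a real consequence: a stated secondary objective on a named value driver has no consistent analysis, and the questionnaire's administration time is stated in two ways. This conclusion rests on the text and on no number. It assumes only that *statically* in 7.3.3 means statistically, which 7.4 and 8.1.1 support, and that the closing clause of the T-test sentences carries its plain meaning.

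The figures of 0.37 to 0.42 SD and 18 percentage points are illustrations under assumed response formats, without clustering. They show that patient responses could be reported with a stated precision, not what that precision will be. The primary time endpoint is unaffected by this point. The change should be made, but the point does not threaten the study's main result.

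**What to change.** 1. In 1.3 and 6.4.1, delete the extension of the T-test to subjective data.
2. In 1.3 and 5.2, drop *significant* from the secondary objective.
3. Make the administration time in 1.3 agree with 6.4.1 and the step lists, which already agree with each other. If a direct question on overall preference is asked, place it after both procedures.
4. Choose one of two routes:
   - **Minimum.** Keep 7.3.3, 7.4 and 8.1.1, and word the objective as describing patient and provider preferences. This removes the contradiction but leaves preference without a stated precision.
   - **Preferred, because preference is a stated value driver.** Amend 7.3.3, 7.4 and 8.1.1 to report patient results as exploratory estimates with 95% intervals. For a direct choice, give the proportion preferring each method. For scaled items, give the within-participant difference by a method suited to the scale: the paired mean difference if numeric, or the proportions rating the scanner better, the same or worse if ordinal. Describe provider responses by clinician, because there are only three, and word the objective to match.

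The minimum route costs wording only. The preferred route adds a short analysis of responses that 7.3.1 already stores by question, methodology and participant. That record does not list the clinician, but the timing record holds both audiologist and participant ID, so the two can be linked. Neither route needs more participants. The response scales must be checked before the method for each item is fixed.
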